Each participant begins 80 sessions of Usual Care to obtain baseline levels, followed by two intervention periods. In the first intervention period (intervention 1, at least 80 sessions), participants will be randomized to one of the four different interventions (A1, A2, B1, or B2). Each research participant will complete at least 80 sessions of the intervention to which they are randomized. At the completion of at least 80 sessions of intervention 1, clinical and neurophysiological assessments will be conducted (Appendix #1). Some assessments may be completed more often.

At the conclusion of the first intervention period, a second intervention period of at least 80 sessions will be commenced. During this second intervention period, participants that had not been receiving weight bearing stand training will be crossed over to receive it. Participants who had been receiving weight bearing training will repeat their current intervention. Thus, participants who had A1 or A2 in intervention 1 would cross over to B1 or B2, respectively, while participants who had B1 or B2 would repeat their intervention.

In what follows it is often convenient to refer to groups (the specific cohort of 9 participants) by their initial intervention in period 1, thus we will refer to groups as A1, A2, B1, or B2, as appropriate.

After at least 80 sessions of the second intervention are completed, assessments are conducted. If an individual does not complete at least 80 sessions of their assigned group intervention, their data will still be evaluated.

Table 1. Interventions for research participants (n=36)

(n=18) Group A		(n=18) Group B	
Intervention #1			
N=9 A1 Vol- scES 6 hours	N=9 A2 CV-scES 6 hours	N=9 B1 Vol-scES 6 hours and Stand-scES + weight bearing training 2 hours	N=9 B2 CV-scES 6 hours and Stand-scES + weight bearing training 2 hours
Intervention #2			
B1 Vol-scES 6 hours and Stand-scES + weight bearing training 2 hours	B2 CV-scES 6 hours and Stand-scES + weight bearing training 2 hours	B1 Vol-scES 6 hours and Stand-scES + weight bearing training 2 hours	B2 CV-scES 6 hours and Stand-scES + weight bearing training 2 hours
Home and Community Integration			

Appendix #1 gives a detailed outline for the timeline and procedures for an individual research participant.

The research participant will be given the choice to have the implant removed by the study neurosurgeon. The neurosurgeon will remove the stimulator if requested by the research participant.

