For those participants not achieving independent standing during the stand training phase of the protocol, the home and community integration will include training in a customized standing device. Standing devices will be designed to match the level of assistance required to safely translate the training to the home environment. This phase can also include training of care givers or personal trainers to assist the participants in achieving safe and independent standing.

G. Statistical approaches.

For the primary aims (comparing to baseline), paired sample t-tests will be used the primary endpoints (hypotheses 1a, 1b, 1c) comparing the results at the end of the second intervention period to the baseline period.

For the secondary aims, each endpoint will be analyzed separately with a common linear model framework. We fit a linear model with effects for each stimulation setting (voluntary, cardiovascular, and standing) and an effect of weight bearing stand training within each stimulation setting. Thus, for example we have a coefficient which measures the additional benefit of weight bearing stand training and a stimulation setting over and above that stimulation setting alone. There are separate coefficients for the benefit of stand training within Vol-scES, CV-scES, and Stand-scES. Formally, we fit a linear model of the form

$$\begin{aligned} \text{Response} = & \beta_{\text{Vol-scES}} I_{\text{Vol-scES}} + \beta_{\text{CV-scES}} I_{\text{CV-scES}} + \beta_{\text{Stand-scES}} I_{\text{Stand-scES}} + \\ & \beta_{\text{VT}} I_{\text{Vol-scES and Training}} + \beta_{\text{CVT}} I_{\text{CV-scES and training}} + \\ & \beta_{\text{ST}} I_{\text{Stand-scES and training}} + \text{error} \end{aligned}$$

where the β terms give the regression coefficients and I_X is an indicator variable equal to 1 if X occurs and 0 otherwise. The indicator variables function to only include the coefficients of the model for treatments the participant actually receives. Thus, for a participant receiving CV-scES and stand training, the model would reduce to

$$\text{Response} = \beta_{\text{CV-scES}} + \beta_{\text{CVT}} + \text{error}$$

Due to the partial crossover, no carryover effects are included in the model (sensitivity analyses using only the first period data will also be summarized). Random effects for each subject may be included when appropriate.

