For hypotheses related to differences between the stimulation settings (hypotheses 1d, 1e, 1f, 3a, 3b), contrasts between the stimulation parameters will be used to test the hypothesis. For example, to test the superiority of CV-scES to the other two settings, the contrasts $\beta_{\text{CV-scES}} - \beta_{\text{Vol-scES}}$ and $\beta_{\text{CV-scES}} - \beta_{\text{Stand-scES}}$ will be used (testing if the difference is greater than 0) if interest centers on stimulation alone, and the contrasts $\beta_{\text{CV-scES}} + \beta_{\text{CVT}} - \beta_{\text{Vol-scES}} - \beta_{\text{VT}}$ and $\beta_{\text{CV-scES}} + \beta_{\text{CVT}} - \beta_{\text{Stand-scES}} - \beta_{\text{ST}}$ if interest centers on stimulation with stand training.

For hypotheses related to the effect of stand training above and beyond stimulation only, the parameters, β_{VT} , β_{CVT} , and β_{ST} may be tested directly (for hypotheses 2a, 2b, 2c)

Comparisons between stimulation frequencies have 90% power to detect effect sizes of 1.7 or higher with size 0.05 (one-sided) tests.

H. Uniqueness of initiative. The present proposal is designed to determine the effectiveness of a novel intervention on the recovery of multiple physiological systems after complete paralysis. There is no current intervention with demonstrated effectiveness in the recovery of motor or autonomic function after complete paralysis except via epidural spinal cord stimulation. The intervention of epidural stimulation applied with our newly developed stimulation parameters is based on a fundamentally sound neurophysiological concept: that the spinal circuitry can be neuromodulated to a physiological state with modest levels of epidural stimulation whereby proprioception itself can contribute to the recovery of the ability to stand and voluntarily control movement below the level of injury. Our experimental strategy embraces a completely new philosophy where the objective is to understand how multiple systems that are normally highly integrated and interdependent respond as such after a severe spinal cord injury, and to establish the efficacy of ES in regaining the ability to:

1. improve cardiovascular function,
2. volitionally control movement,
3. stand independently
4. improve bowel and bladder function,
5. improve sexual function
6. improve respiratory function,
7. improve quality of life, and
8. reduce health care costs.

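### The secondary linear model pools both periods without a period term, so the stand-training coefficients for 2a and 2b absorb about two thirds or more of any gain from continued stimulation

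*Protocol*

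**What the plan says.** Protocol III.G writes the secondary model out as a formula. It has three stimulation indicators, three stimulation-with-training indicators and an error term: "We fit a linear model with effects for each stimulation setting (voluntary, cardiovascular, and standing) and an effect of weight bearing stand training". The indicators record treatment only: "The indicator variables function to only include the coefficients of the model for treatments the participant actually receives". Carryover terms are expressly left out, and III.G adds that "sensitivity analyses using only the first period data will also be summarized", so the main fit uses both periods. On repeated observations it says: "Random effects for each subject may be included when appropriate".

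III.B.4 sets the sequence. In the second period, of at least 80 sessions, "participants that had not been receiving weight bearing stand training will be crossed over to receive it". For the others: "Participants who had been receiving weight bearing training will repeat their current intervention".

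Hypotheses 2a and 2b ask whether stand training adds to Vol-scES and to CV-scES. Their methods paragraphs in III.C name the corresponding training coefficient as the test. III.G gives the same route: "For hypotheses related to the effect of stand training above and beyond stimulation only", the coefficients beta_VT and beta_CVT may be tested directly.

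**The concern.** Nobody receives stimulation without stand training in period 2. Training status is therefore tangled with time on stimulation, and the model has no term to separate the two. If sessions 81 to 160 of Vol-scES or CV-scES bring any further gain of their own, the model has to credit most of it to stand training.

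One declared purpose of the trial is to learn whether stand training is needed on top of stimulation. The stated main analysis for that question can answer yes when only longer stimulation helped. Omitting carryover does not cover this, because carryover and period are different effects.

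**Working it through.** **The plan's own figure.** III.G claims 90% power for an effect size of 1.7 between stimulation settings, one-sided 5%. With 6 per group, 1.7/sqrt(2/6) = 2.944, and 2.944 - 1.645 = 1.299 gives 90.3%, so the figure reproduces (normal approximation). It rests on the 6 per group of III.B rather than the 9 of III.B.4. It concerns a different comparison and does not bear on this point.

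**Inputs.** III.B.4: 9 people in each of A1, A2, B1 and B2, two periods. Assumed here: one observation per person per period (72 rows), total SD 1, within-person correlation rho (ICC), and a gain delta added to every period-2 response. The protocol gives neither rho nor delta, so both are varied.

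**Layout within one setting (Vol or CV).**

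| | Period 1 | Period 2 |
|---|---|---|
| No training | 9 (Group A) | 0 |
| With training | 9 (Group B) | 9 (A) + 9 (B) = 18 |

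**Bias by ordinary least squares.** The untrained mean carries none of delta. The trained mean carries 18/27 of it. Bias in beta_VT and in beta_CVT = 18/27 delta = 0.667 delta.

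**Bias with a random intercept but no period term.** The share is 2(1 + rho)/(3 + rho):

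- rho 0.3: 2.6/3.3 = 0.788
- rho 0.5: 3.0/3.5 = 0.857
- rho 0.7: 3.4/3.7 = 0.919

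The share tends to 1 as rho approaches 1. Adding the optional subject effect alone therefore makes the bias larger. Contrasts between CV and Vol get zero bias from a period effect common to both settings.

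**Rejection of a true null** (no training effect, beta_CVT, one-sided 5%, 20,000 simulations per cell; ranges over rho 0.3 to 0.7):

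| delta (SD) | Least squares | Mixed, no period | Mixed with period |
|---|---|---|---|
| 0 | 3.1-4.3% | 4.9-5.0% | about 5% |
| 0.1 | 4.5-6.0% | 7.7-10.3% | about 5% |
| 0.2 | 7.4-8.5% | 11.5-18.0% | about 5% |
| 0.3 | 9.8-11.5% | 16.0-28.0% | about 5% |
| 0.5 | 17.9-19.4% | 28.2-53.5% | about 5% |

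The last column lay between 4.7% and 5.3% in every cell.

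**Can a period effect be estimated?** Yes. Group B repeats its intervention, so its change between periods shows the period effect. The four estimable columns (Vol, CV, and training within each) plus period have rank 5. The six-coefficient formula has rank 4, because no arm receives Stand-scES without training or without Vol- or CV-scES. III.G's own worked example, CV-scES with stand training, contains no Stand coefficient.

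**Precision of the training effect (SE, in SD units).**

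| rho | Mixed, no period | Mixed with period | Ratio |
|---|---|---|---|
| 0.3 | 0.350 | 0.403 | 1.15 |
| 0.5 | 0.309 | 0.362 | 1.17 |
| 0.7 | 0.248 | 0.295 | 1.19 |

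Period 1 only: sqrt(2/9) = 0.471. For a true 1 SD training effect at rho 0.5, power by noncentral t is 67% with period 1 only and 86% with the pooled model plus period.

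**Separate, smaller point: leaving out the subject effect.** The trained group in each setting has 27 rows, of which 18 are pairs from 9 people. The variance of the with-training CV-versus-Vol contrast is then understated by a factor of 1 + 18 rho/27, which is 1.33 at rho 0.5 and 1.47 at 0.7. The simulated size of that test is 7.4% and 8.9% instead of 5%.

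**The case against.** - **The protocol already plans an unbiased check.** The first-period-only analysis is a randomised parallel comparison and is free of this bias. That is true, but it is only a sensitivity analysis. It does not decide 2a and 2b, and it is the least precise of the pooled and unpooled options compared here.
- **The reach is limited.** The primary-endpoint tests (1a to 1c) are paired t-tests outside this model, and CV-versus-Vol contrasts are untouched by a common period effect. This stands. The error reaches 2a and 2b, and 3b so far as it relies on beta_CVT.
- **Two thirds is not a strict floor.** It assumes complete data. Under least squares, with 7 of 9 remaining per sequence in period 2, the share is 14/23 = 0.61. With 6 of 9 it is 12/21 = 0.57. This qualifies the figure modestly.
- **The large error rates need assumptions.** The 28-54% figures require the optional random intercept and an assumed 0.5 SD gain. For the formula as written, a gain of 0.1 to 0.2 SD gives only 4.5-8.5%. That is fair, and it is why the full range is shown.
- **The sign of delta is assumed.** III.G does not define the response. If it were gain within each period, a plateau would make delta negative and the test conservative. The share absorbed is the same for either sign, so the coefficient would still be wrong.
- **The remedy has its own assumption.** Group B's second period adds stand training as well as stimulation. If that brings Group B an extra gain, the corrected training coefficient is too small by 0.3 to 0.7 of the extra (ICC 0.3 to 0.7). This stands as a real limit. The error is in the conservative direction, but it could hide a true effect.

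**Conclusion.** The concern holds. As written, the main secondary analysis misattributes a period-2 gain to stand training. With complete data on 9 people per arm, the share is 0.67 by least squares and 0.79 to 0.92 with a random intercept at ICC 0.3 to 0.7. How far this distorts the tests of 2a and 2b depends on delta, which the protocol does not give. The effect is slight at 0.1 SD and serious at 0.5 SD. The design offers no reason to take delta as zero over a further 80 or more sessions. The formula is stated in the protocol, so this is not a detail left open for a later plan. Because only secondary hypotheses are involved and an unbiased sensitivity analysis exists, the model should be corrected, but the point does not threaten the primary analysis.

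**What to change.** Replace the III.G formula with:

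Response = beta_Vol-scES + beta_CV-scES + beta_VT + beta_CVT (each applied through its indicator) + a fixed period-2 effect + a random subject intercept + error.

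- Always include the subject intercept, and only together with the period term.
- State the assumption that the period-2 effect is common to Groups A and B and, as a single term, to both settings.
- Keep the first-period-only fit as the sensitivity analysis. It would help to show a failure of the common-period assumption.
- State that beta_Stand-scES and beta_ST are omitted because the design cannot estimate them. Say also that the Stand-scES coefficient tests named for 1d, 1e and 1f therefore cannot come from this model. No test that the model could have delivered is lost.

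**Cost.** The change affects analysis wording only and needs no new data. The standard error of the training effect rises by 15-19% against the mixed model without period, and stays below the 0.471 SD of the first-period-only analysis.

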B. Experimental Design: We will enroll, implant and complete the interventions in 36 research participants who have sustained a SCI in the proposed experiments. We anticipate we will need to screen 108 potential research participants to enroll 36 individuals who will complete the study. This sample size will provide sufficient replication per study group (n=6) from which variance and effect size estimates for each study hypothesis can be calculated, and hypothesis tests conducted. We will also select individuals to assure that there are a minimum of 25% (n=9) women to adequately represent the percentage in the SCI population. We will study each cohort of patients comprehensively, and each individual will be allocated to the group interventions based on the method of minimization. Research participants will be randomized into group interventions. Our novel approach of conducting repeated experiments with comprehensive assessments in a smaller cohort of patients, rather than a more traditional approach of including a large number of patients and focusing on a single outcome, will advance both clinical and scientific knowledge in this highly complex population. We have found success with the smaller cohort approach because we can employ more rigorous, quantitative and sensitive outcomes that not only inform us about the potential clinical efficacy, but also provide further knowledge of the mechanisms of neural control of movement and other physiological mechanisms related to cardiovascular, respiratory, bladder, bowel and sexual function.

1. Recruitment, pre-screening, screening and enrollment

a. Recruitment. Potential research participants will be identified by our research database (UofL IRB 06.0647) that currently contains over 6,000 individuals.

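### The section G model for the secondary aims leaves Response undefined and omits the participant's pre-intervention value, so the contrasts between stimulation settings lose precision that data already collected could supply

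*Protocol*

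**What the plan says.** Protocol III.G sets one approach for the secondary aims: "For the secondary aims, each endpoint will be analyzed separately with a common linear model framework". The model is described as follows: "We fit a linear model with effects for each stimulation setting (voluntary, cardiovascular, and standing) and an effect of weight bearing stand training". It is then written out in full as three stimulation indicators, three stimulation-and-training indicators and error. The worked example, for a participant on CV-scES with stand training, reduces to two coefficients and error. Neither the rest of III.G nor the Methods paragraphs under the hypotheses in III.C add a baseline term or any other covariate. Response is not defined as a level or as a change. Subject effects are optional: "Random effects for each subject may be included when appropriate". A sensitivity analysis restricted to the first period is also planned.

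Baseline data exist. III.B.4 says: "Each participant begins 80 sessions of Usual Care to obtain baseline levels, followed by two intervention periods". Appendix 1 schedules measurements before the intervention at Screen, Pre-Usual Care, Pre-implant or Post-Implant/Pre-Intervention, depending on the outcome. Within III.G, baseline enters only the paired t-tests for 1a, 1b and 1c.

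Arms are small. III.B.4 refers to "groups (the specific cohort of 9 participants) by their initial intervention in period 1". On allocation, III.B says "each individual will be allocated to the group interventions based on the method of minimization" and names no factors.

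**The concern.** Hypotheses 1d, 1e and 3a compare Vol-scES with CV-scES, which different people receive. Hypotheses 1e and 3a are worded as improvements, yet the printed model does not contain the value from which a person improved. With 9 per arm, in a population admitted on several different patterns of blood pressure dysfunction (inclusion criterion 7), between-person spread may be wide and two arms can start apart by chance. Minimization on unnamed factors does not assure balance on each outcome's own baseline. A model without that value leaves this spread in the error term and lets part of any chance difference pass into the estimated contrast. At stake are wider intervals and lower power in comparisons that are already small.

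**Working it through.** **Inputs.** From the protocol: 9 per arm and four arms (III.B.4, Table 1); one-sided 0.05 and 90% power (III.G). Assumed: baseline-outcome correlation rho, which the protocol does not give, taken as 0 to 0.8; equal SD at each time; and, for the two-period model, the same rho between any two time points.

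**1. The plan's own figure.** III.G states: "Comparisons between stimulation frequencies have 90% power to detect effect sizes of 1.7 or higher with size 0.05 (one-sided) tests". A two-group normal approximation with the 6 per group named in III.B gives 1.7 x sqrt(6/2) - 1.645 = 1.300, so power is 90.3%. The stated figure is thus an unadjusted comparison with no allowance for baseline. With 9 per arm the same formula gives 1.7 x sqrt(9/2) - 1.645 = 1.961, or 97.5%. The mismatch of 6 and 9 is a separate matter.

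**2. Chance imbalance.** The SD of the baseline difference between two arms of 9 is sqrt(2/9) = 0.471 outcome SD. Under simple randomization it exceeds 0.5 SD in either direction with probability 29% and 1 SD with probability 3.4%. A fraction rho of it carries into an unadjusted contrast.

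**3. One period, 9 per arm.** Error df pooled over four arms are 36 - 4 = 32. Without baseline, the effect detectable with 90% power from the non-central t is 1.41 SD, and power at 1.0 SD is 67%. With the covariate, the residual variance factor is 1 - rho^2. It is multiplied by about 1 + 1/30 for estimating the slope, and df fall to 31. For example, at rho = 0.5: 0.75 x 1.033 = 0.775, and 1.41 x sqrt(0.775) = 1.24.

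| rho | 1 - rho^2 | with slope cost | detectable effect (SD) | power at 1.0 SD |
|---|---|---|---|---|
| no covariate | - | - | 1.41 | 67% |
| 0 | 1.00 | 1.03 | 1.43 | 65% |
| 0.3 | 0.91 | 0.94 | 1.37 | 69% |
| 0.5 | 0.75 | 0.78 | 1.24 | 76% |
| 0.7 | 0.51 | 0.53 | 1.02 | 89% |
| 0.8 | 0.36 | 0.37 | 0.86 | 96% |

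**4. Two periods with a subject random effect.** Within each stimulation setting, 9 participants have stimulation alone and then with training, and 9 have training in both periods. Let V be the 2 x 2 covariance of the two outcomes (1 on the diagonal, rho off it). Conditioning on baseline replaces V by V - rho^2 J, where J is the all-ones matrix. At rho = 0.5, the information matrix for the two means (alone, with training) is:

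- without baseline: [[12, -6], [-6, 24]], so the variance of the stimulation-alone mean is 24/252 = 0.0952 and of CV minus Vol 0.1905;
- with baseline: [[13.5, -4.5], [-4.5, 31.5]], giving 31.5/405 = 0.0778 and 0.1556.

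The ratio is 0.1556/0.1905 = 0.82. Variance ratios across rho, before the small slope cost:

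| rho | CV vs Vol, stimulation alone | CV vs Vol, with training | training coefficient (2a, 2b) |
|---|---|---|---|
| 0.3 | 0.93 | 0.88 | 0.97 |
| 0.5 | 0.82 | 0.70 | 0.93 |
| 0.7 | 0.63 | 0.46 | 0.90 |
| 0.8 | 0.48 | 0.32 | 0.89 |

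So the optional random effect does not replace the covariate in the between-setting contrasts. It does most of the work for the training coefficients, where much of the information is within person.

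**5. If Response means change from baseline.** The variance factor is 2(1 - rho): 1.4 / 1.0 / 0.6 / 0.4 at rho 0.3 / 0.5 / 0.7 / 0.8, against 0.91 / 0.75 / 0.51 / 0.36 with the covariate. The difference is (1 - rho)^2, which is never negative. Detectable effects would be 1.41 x sqrt(2(1 - rho)) = 1.67 / 1.41 / 1.09 / 0.89.

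**The case against.** **Response may already be a change score.** The hypotheses speak of improvement and the model has no intercept, which suits a change better than a raw blood pressure. A reader might infer that the contrasts compare raw post-treatment levels; the text does not establish that. If change is meant, most of the gain at rho 0.7-0.8 is already there (1.09 and 0.89 against 1.02 and 0.86). What remains is that Response is undefined, and that the covariate is at least as precise under either reading once rho is clear of zero.

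**Covariates are often left to an SAP.** This is true, and the SAP is not at hand. But the protocol prints the complete formula and a worked reduction of it, so it has fixed a model without the term.

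**Randomization protects the comparison.** This stands. The unadjusted contrast is not systematically biased, and its standard error already reflects chance imbalance.

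**The correlations are assumed.** This also stands. Entry requires inability to move the leg joints voluntarily and to stand independently (inclusion criteria 5 and 6), so stimulation-off motor and standing baselines may lie near a floor, with low rho and little gain.

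**Scope.** It would be too much to say that every secondary hypothesis is affected or that baseline is otherwise unused. Hypotheses 1b and 1c are labelled secondary in III.C but are tested against baseline by paired t-test. Echocardiography (III.D.2.c) is also compared from baseline to end of training.

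**Conclusion.** The concern holds as a loss of precision in a model that the protocol has written out. It falls mainly on 1d, 1e and 3a and on the first-period sensitivity analyses. At an assumed correlation of 0.5 to 0.8, the one-period detectable effect falls from 1.41 SD to between 1.24 and 0.86, and the two-period CV-vs-Vol variance for stimulation alone falls by 18% to 52%. At 0.3 the gain is slight, and at 0 there is a slight loss (1.43 against 1.41). Two stronger conclusions are not supported: that the contrasts are biased, and that 2a and 2b suffer to the same degree, since with a subject random effect those coefficients gain only about 3-11%. The benefit is likely to be clearest for the cardiovascular and autonomic outcomes (1e, 3a), and it matters for effects below about 1.4 SD rather than at the planned 1.7.

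**What to change.** In III.G:

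- Define Response as the post-intervention value of the outcome.
- Add as a covariate the same outcome's last stimulation-off value before the intervention. This is the Pre-implant or Post-Implant/Pre-Intervention value where scheduled, and otherwise the Pre-Usual Care or Screen value. The fallback is needed: Appendix 1 marks ambulatory blood pressure and heart rate before treatment only at Screen and Pre-Usual Care.
- Make the subject random effect a fixed part of the two-period model rather than an option.
- Use the same covariate in the first-period sensitivity analysis.
- Restate the detectable effect for 9 per arm, with the assumed correlation shown.

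The cost is wording and one degree of freedom per model, with a slight loss of precision where the correlation is near zero. No new measurements are needed.
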